7.1.1 Liver Chemistry Stopping Criteria

There is no preclinical or clinical evidence that balovaptan administration is associated with an increase in abnormal liver tests.

Discontinuation of study treatment is required by the investigator when a study participant meets abnormal liver tests as outlined Appendix 3 (see Section A3–7.6), or if

the investigator believes that it is in best interest of the participant when abnormal liver chemistries not meeting protocol-specified stopping rules.

Discontinuation of study treatment is also required if the participant experiences moderate or severe hepatic impairment, defined as Child-Pugh class B (7–9 points) and class C (10–15 points), respectively. Please see [Appendix 8](#) for Child-Pugh classification.

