- ^k Urine samples will be analyzed for the presence of drugs such as: alcohol, cannabinoids, opiates, cocaine, barbiturates, methadone, and PCP. Results will be used to verify participant eligibility pertaining to drugs of abuse. Inconclusive results may be repeated once during the screening period. Investigators should use their best clinical judgment in cases where results may be erroneous (e.g., permitted use of opiates or ingestion of food or food supplements).
- ^l Viral serology includes HIV (specific tests for HIV-1 antibody, HIV-1 and -2 antibodies, and HIV-2 antibody), HBsAg, HBcAb, and HCV antibody.
- ^m Coagulation assessments include INR, aPTT, and PT.
- ⁿ Females of childbearing potential (including those who have had a tubal ligation) will have a serum pregnancy test at screening and must have a urine pregnancy test performed at the site prior to each dose administration at the specified visits. If a urine pregnancy test is positive, it must be confirmed by a serum pregnancy test at the central laboratory. Results are to be recorded only in the source documents.
- ^o Vital signs include measurements of respiratory rate, pulse rate, and systolic and diastolic blood pressure while the participant is in a seated position, and body temperature. Vital sign assessments should be performed just prior to study drug administration. All vital signs should be recorded on the eCRF. *Three consecutive blood pressure readings will be recorded at intervals of at least 1 minute. The average of the three blood pressure readings will be recorded on the eCRF.*
- ^p PK samples should be obtained just prior to study drug administration, if possible. At Week 6, two PK samples will be taken (pre- and post-dose). Following the pre-dose sample, at the start of the study visit, the participant will receive study drug. A post-dose sample can be taken at any time between 3 hours after study drug administration and the end of the study visit. Accurate recording of the time of study drug administration and sample collection is critical.
- ^q Can be collected on any study visit if not collected at baseline visit.
- ^r Not applicable for a site that has not been granted approval for WGS.
- ^s Not applicable for a site that has not been granted approval for RBR sampling. Perform only for participants at participating sites who have provided written informed consent to participate.

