- Participants who meet any of the following criteria related to other organ systems will be excluded from the study:
 - Positive serology results for hepatitis B surface antigen (HBsAg), hepatitis B core antibody (HBcAb), hepatitis C virus (HCV) antibody, or HIV-1 or HIV-2
 - All participants must have a negative HBsAg result and negative hepatitis C antibody screening tests prior to enrollment. If total HBcAb is positive at screening, hepatitis B virus (HBV) DNA measured by polymerase chain reaction must be negative to be eligible.
 - Moderate or severe hepatic impairment defined as Child-Pugh class B (7–9 points) and class C (10–15 points), respectively (see [Appendix 8](#))
 - Moderate or severe renal impairment defined as estimated glomerular filtration rate (eGFR) based on serum creatinine value of: < 60 mL/min/1.73m²
 - Evidence of current or past gastrointestinal (GI) disease that could potentially limit the absorption of study drug or pose unacceptable risks in the opinion of the investigator (e.g., GI bleeding, active stomach ulcer)
 - History of coagulopathies, bleeding disorders, blood dyscrasias, hematological malignancies, myelosuppression (including iatrogenic)
 - Concomitant disease or condition that could interfere with, or treatment of which might interfere with, the conduct of the study, or what would, in the opinion of the investigator, poses an unacceptable risk to the participant in this study
 - Confirmed clinically significant abnormality in parameters of hematology (e.g., a neutrophil count of <1500/ μ L; in case of assumed "benign ethnic neutropenia," a count of <1300/ μ L constitutes exclusion)
 - Confirmed clinically significant abnormality in parameters of clinical chemistry, coagulation, or urinalysis

- Medical history of malignancy, if not considered cured
- Participants who meet any of the following exclusion criteria will be excluded from the study:
 - Participants who have received treatment with investigational therapy within 8 weeks prior to randomization
 - Known hypersensitivity to balovaptan, its components, or any of the excipients used in the formulation
 - Any other condition and/or situation that the Investigator believes may interfere with the safety of the participant, study conduct, or interpretation of study data (safety or efficacy endpoints)

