7.1 DISCONTINUATION OF STUDY TREATMENT

It may be necessary for a participant to permanently discontinue (definitive discontinuation) study treatment. If study treatment is definitively discontinued, the

participant will remain in the study for additional assessments. Refer to the schedule of activities (see Section 1.3) for data to be collected at the time of discontinuation of study treatment and for any further follow-up evaluations that need to be completed.

Participants must permanently discontinue study treatment if they experience any of the following:

- Any medical condition that the investigator or Sponsor determines may jeopardize the participant's safety if he or she continues to receive study treatment
- Investigator or Sponsor determination that treatment discontinuation is in the best interest of the participant
- Pregnancy
- Inability of participant to continue to comply with study requirements
- Suicidal ideation score of 4 or 5 or category 6 or greater on the C-SSRS
- Specific events that are described in Sections 7.1.1, 7.1.2, 7.1.3, and 7.1.4

The primary reason for study treatment discontinuation should be documented on the appropriate eCRF.

All participants who withdraw or discontinue from the study treatment early will be asked to return as soon as possible (and within 2 weeks after the last dose of study drug) for an early discontinuation visit and complete the assessments as per the schedule of activities in Section 1.3 (see Table 1). Participants will also be asked to return for assessments of the primary and secondary efficacy outcomes at the end of the 12-week planned visit, regardless of their adherence to treatment. If the time between the early discontinuation visit and the 12-week planned visit is fewer than 2 weeks, then participants are exempted from the 12-week planned visit. If the time between the early discontinuation visit and the previous visit is fewer than 2 weeks, then participants are exempted from completing again all the primary and secondary assessments at the early discontinuation visit.

Refer to the schedule of activities in Section 1.3 (see Table 1) for details on follow-up assessments to be performed for participants who permanently discontinue study treatment. If a participant requests to be withdrawn from treatment or follow-up assessments, this request must be documented in the source documents and signed by the investigator.

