In case of emergent neutropenia, treatment discontinuation is suggested for participants who meet the following criterion for decreased ANC:

- If the ANC falls $<800/\mu\text{L}$ and the low ANC is confirmed in a second sample to be obtained within about 3 days, the investigator should consider treatment discontinuation. In cases of ANC-related treatment discontinuation, additional laboratory parameters should be considered by the investigator, including fibrinogen, high-sensitivity C-reactive protein (hs-CRP), and an assessment for anti-neutrophil cytoplasmic antibody (ANCA).
- Follow-up management of participants who experience fever and/or infection in the context of reduced ANC should be discussed with the Medical Monitor and the participant may be referred to a specialist to decide on next steps.

ANC values below $800/\mu\text{L}$ (confirmed), should be reported as an adverse event of special interest (see [Appendix 3](#), Section [A3–5](#)).

A6–2.5 MANAGEMENT OF BLEEDING

While the risk of bleeding events due to balovaptan is considered low, should such an event occur, a review of concomitant medications should be undertaken especially those that have known bleeding risks. Based on the clinical significance of the bleeding, treatment with study drug should be interrupted and may be permanently discontinued if no alternative causative factors of the bleeding adverse event can be identified and removed.

Blood samples to assess coagulation parameters (INR, PT, aPTT) as well as balovaptan blood levels should be taken.

A6–2.6 MANAGEMENT OF SKELETAL MUSCLE TOXICITY

Elevated CPK levels at screening and baseline are not exclusions as long as serum creatinine and potassium values do not exceed the upper limit of normal (ULN). In instances where CPK is increased more than $2\times\text{ULN}$ at screening, additional CPK, creatinine, and potassium samples should also be obtained at Week 2 of treatment. Samples from screening, baseline, Week 2, and Week 6 can then indicate whether an elevated CPK level observed at screening is part of a fluctuation because of physical exercise, for example, or is indicative of inherently elevated CPK levels in an individual participants. Participants are advised to abstain from intense physical exercise and to report musculoskeletal adverse events to the Investigator promptly.

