Appendix 8 Child–Pugh Classification

Hepatic impairment will be classified according to the Child-Pugh system (Table A8-1), and the parameters to determine Child-Pugh classification for each participant will be collected at Screening.

Table A8-1 Child–Pugh Classification of Hepatic Function

	Points Scored for Observed Findings		
	1	2	3
Hepatic encephalopathy grade ^a	0	1 or 2 ^b	3 or 4 ^b
Ascites ^c	Absent	Slight	Moderate
Serum bilirubin, mg/dL (μmol/L)	<2 (<34)	2 to 3 (34 to 50)	>3 (>50)
Serum albumin, g/dL (g/L)	>3.5 (>35)	2.8 to 3.5 (28 to 35)	<2.8 (<28)
International normalized ratio	<1.7	1.7 to 2.3	>2.8

Note: Chronic hepatic impairment is classified into Child-Pugh class A to C, employing the added score of the 5 parameters described above.

Severe impairment (Child-Pugh class C): 10 to 15 points

Moderate impairment (Child-Pugh class B): 7 to 9 points

^a In this study (BN43546), hepatic encephalopathy will be graded according to the following criteria:

Grade 0: normal consciousness, personality, neurological examination, or normal electroencephalogram.

Grade 1: restless, sleep disturbed, irritable/agitated, tremor, impaired handwriting, or 5 cycles per second (cps) waves.

Grade 2: lethargic, time-disoriented, inappropriate, asterixis, ataxia, or slow triphasic waves.

Grade 3: somnolent, stuporous, place-disoriented, hyperactive reflexes, rigidity, or slower waves.

Grade 4: unarousable coma, no personality/behavior, decerebrate, or slow 2 to 3 cps delta activity.

^b Subjects with hepatic encephalopathy Grade 2 or above will not be enrolled into the study.

^c Subjects with evidence of severe ascites will not be enrolled into the study. Ascites will be graded according to the following criteria:

Absent: no ascites is detectable by manual examination or by ultrasound investigation (if performed).

Slight: ascites palpitation doubtful, but ascites measurable by ultrasound investigation (if performed).

Moderate: ascites detectable by palpitations and by ultrasound investigation (if performed).

Severe: necessity of paracentesis; does not respond to treatment.

Appendix 9

Questionnaire to Evaluate for Signs and Symptoms Indicative of Infections

The following questionnaire will be used to evaluate signs and symptoms indicative of infection in participants either by telephone interview or in-person between site personnel and the participant at Weeks 4, 6, 9, and 12.

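### Table A8-1 gives no Child-Pugh points for an INR above 2.3 up to 2.8, so the class B/C limit used for exclusion and mandatory stopping cannot be computed there (low severity)

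*Combined protocol and SAP*

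**What the plan says.** Section 7.1 introduces its list of binding stops with "Participants must permanently discontinue study treatment if they experience any of the following", and that list includes the events in 7.1.1. Section 7.1.1 adds the hepatic rule: "Discontinuation of study treatment is also required if the participant experiences moderate or severe hepatic impairment". It defines those grades as Child-Pugh class B (7 to 9 points) and class C (10 to 15 points) and sends the reader to Appendix 8 for the scoring.

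Section 5.2 uses the same classes to exclude at entry: "Moderate or severe hepatic impairment defined as Child-Pugh class B (7–9 points) and class C (10–15 points), respectively". Appendix 8 says that the Child-Pugh items are collected at screening and that the class comes from the sum of five items.

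The INR row of Table A8-1, with its 1-, 2- and 3-point cells in order, reads "International normalized ratio <1.7 1.7 to 2.3 >2.8".

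On the source of INR values, footnote m to Table 1 in Section 1.3 says "Coagulation assessments include INR, aPTT, and PT". Table 1 schedules coagulation at screening, Week 12 and early discontinuation. Appendix 6, A6-2.5, adds an unscheduled route after a bleeding event: "Blood samples to assess coagulation parameters (INR, PT, aPTT) as well as balovaptan blood levels should be taken".

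**The concern.** A numeric threshold that excludes a candidate or permanently stops drug should return an answer for every value that can be entered. Here one of the five inputs has an interval with no points. The other two laboratory rows of the table have no such hole: in each, the 3-point band starts where the 2-point band ends. I found no other place in the documents that gives an INR band or a rule for an unscored value.

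What is at stake is consistency between sites. About 12 sites would apply the table, and Section 5 does not permit prospective waivers of entry criteria. Two sites with the same laboratory values could reach opposite decisions, one reading the gap as an extension of the 2-point band and the other as the start of the 3-point band.

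**Working it through.** **Inputs.** From Table A8-1 and its notes: five items, each scoring 1, 2 or 3; class B at 7 to 9 points; class C at 10 to 15. From 7.1.1 and 5.2: stop or exclude at class B or C.

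**Step 1, reproduce the scale.** Let T be the sum of the five items. The minimum is 5 × 1 = 5 and the maximum is 5 × 3 = 15, which agrees with the stated upper limit of class C. Totals of 5 and 6 fall below class B. The rule is therefore: stop or exclude if T ≥ 7.

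**Step 2, locate the gap.**

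| Row | 1 point | 2 points | 3 points | Bands meet? |
|---|---|---|---|---|
| Bilirubin, mg/dL | <2 | 2 to 3 | >3 | yes |
| Albumin, g/dL | >3.5 | 2.8 to 3.5 | <2.8 | yes |
| INR | <1.7 | 1.7 to 2.3 | >2.8 | no |

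The unscored interval is above 2.3 up to and including 2.8, a width of 2.8 − 2.3 = 0.5. Assuming that INR is reported to one decimal, five values have no score: 2.4, 2.5, 2.6, 2.7 and 2.8. The neighbours do: 2.3 scores 2 and 2.9 scores 3.

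**Step 3, find where the decision changes.** Let S be the sum of the other four items, so S runs from 4 to 12 over 3^4 = 81 patterns. An INR in the gap should score 2 or 3, the points of the bands on either side.

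- Gap read as 2 points: T = S + 2, and T ≥ 7 needs S ≥ 5. This holds in 80 patterns.
- Gap read as 3 points: T = S + 3, and T ≥ 7 needs S ≥ 4. This holds in all 81.
- The decision differs only at S = 4, which is one pattern (all four items at 1 point): 4 + 2 = 6, continue, against 4 + 3 = 7, stop.

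In a further 16 patterns (S = 7) the class is unclear, 9 points (B) against 10 (C), but both classes require the same action. These are counts of patterns, not probabilities for patients.

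**Step 4, test the assumption in step 3.** If a site scored the gap as 1, the patterns open to dispute would be those with S = 4 or 5: 1 + 4 = 5. If a site left the item out and counted 0, they would be those with S = 4, 5 or 6: 1 + 4 + 10 = 15. Neither reading is sensible, because each gives a higher INR fewer points than a lower one.

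**Step 5, ask when a gap value could arise.**

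- Screening: INR is scheduled and the score is used for 5.2.
- Weeks 2 to 9: no coagulation test is scheduled.
- Week 12 and early discontinuation: INR is scheduled, but dosing is ending or over.
- Any time on treatment: an unscheduled INR, for example under A6-2.5.

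**The case against.** The strongest reply is that the gap is an editorial slip with almost no room to do harm. Most of it stands.

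- **Entry is largely covered.** Section 5.2 separately excludes "Confirmed clinically significant abnormality in parameters of clinical chemistry, coagulation, or urinalysis" and a history of coagulopathies or bleeding disorders. A candidate with a confirmed INR of 2.5 would probably fail on those grounds. The cover is not complete, since clinical significance is a judgment and the Child-Pugh limit is meant to be a number.
- **The bleeding route has its own rule.** A6-2.5 already tells the site to interrupt drug according to the clinical significance of the bleed. It leaves permanent discontinuation optional, so the mandatory rule in 7.1.1 would still add something.
- **Discretion exists.** Sections 7.1 and 7.1.1 let the investigator stop drug on safety grounds or in the participant's interest. Only the mandatory rule is undecided.
- **The affected pattern is a doubtful liver case.** It is an isolated INR rise with bilirubin, albumin, ascites and encephalopathy all at their best score, and the table note speaks of chronic impairment. That is a fair clinical point, but the table as written still has to return a score.
- **One digit carries the point.** The cell was read from a PDF by machine. The row is intact, but an 8 read for a 3 cannot be ruled out from the text alone.
- **The analysis is barely touched.** About 30 participants are summarised descriptively, those who stop drug remain in the study for assessments, and the clinical question is posed irrespective of adherence.

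A reader might infer that the hepatic stopping rule fails on treatment, or that participants with liver impairment would be kept on drug. The documents do not support that: once any other item scores above 1, the stop follows whether the gap is read as 2 or 3, and no scheduled INR falls in mid-treatment. A reader might also infer that the documents show above 2.3 to be the correct cut-point. They do not. Extending the 2-point band to 2.8 would close the gap equally well.

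**Conclusion.** The point holds in a narrow form and is of low severity. As the text reads, Table A8-1 leaves an INR above 2.3 up to 2.8 without points, so the class B/C threshold behind both the 5.2 exclusion and the 7.1.1 stop is not computable for those values. The outcome is truly undecided in one score pattern of 81, the one with a total of 6 or 7.

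This rests on three assumptions: the cell is printed as it reads in the text; a gap value would take the points of a neighbouring band; and, for the count of five values, INR is reported to one decimal. The documents give no frequency for an isolated INR in this range, so no number of affected participants can be stated. What justifies a correction is that the figure sits inside a binding rule and costs almost nothing to repair.

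**What to change.** First, check the INR cell of Table A8-1 against the source document. If it reads above 2.3 there, nothing needs to change.

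If it reads above 2.8, change the 3-point INR cell to above 2.3. The bands then meet, as they do for bilirubin and albumin, and the disputed pattern resolves in the cautious direction (4 + 3 = 7, class B). The sponsor should confirm that this is the intended cut-point, because the alternative of running the 2-point band to 2.8 gives the opposite decision (4 + 2 = 6).

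The cost is one table cell, with no added test or visit. The downside is that a rare isolated INR of 2.4 to 2.8 would then exclude a candidate or permanently stop drug, and Section 7 asks sites to avoid unnecessary withdrawals.

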1.3 SCHEDULE OF ACTIVITIES

Table 1 Schedule of Activities

	Screening	Pre-Rand. Visit	Blinded Treatment Period						Safety Follow-Up ^a	Early Discont. ^{b, c}
Week			0	2	4 ^d	6	9 ^d	12	14	
Study Day(s)	-28 to -1	-7 to -1	1	14	28	42	63	84	98	
Visit window (days)				±3	±3	±3	±3	±3	-3/+7	
Informed consent ^e	x									
Medical history, demographics, and baseline conditions ^f	x									
Resting-state EEG ^g		x ^h		x		x		x		x ⁱ
Urinalysis ^j	x								x	x
Urinalysis for substance abuse ^k	x		x			x		x	x	x
Serology (HIV, and hepatitis B and C) ^l	x									
Coagulation ^m	x							x		x
Pregnancy test ⁿ	x		x			x		x		x
Weight and height (height to be measured at screening only)	x							x		x
Vital signs ^o	x		x	x		x		x	x	x
PK blood sample ^p				x		x		x		x
Clinical genotyping sample ^q			x							
Blood sample for WGS ^r			x							
RBR blood sample (optional) ^s				x						

Table 1 Schedule of Activities (cont.)

	Screening	Pre-Rand. Visit	Blinded Treatment Period						Safety Follow-Up ^a	Early Discont. ^{b, c}
Week			0	2	4 ^d	6	9 ^d	12	14	
Study Day(s)	-28 to -1	-7 to -1	1	14	28	42	63	84	98	
Visit window (days)				±3	±3	±3	±3	±3	-3/+7	
Complete physical examination ^t	x		x					x	x	x
Limited physical examination ^t						x				
Neurologic evaluation (upper and lower limbs)	x		x			x		x	x	x
Clinical signs and symptoms of infection ^u					x	x	x	x		
12-Lead ECG ^v	x		x	x				x	x	x
Hematology ^w	x		x			x		x	x	x
Full serum chemistry ^x	x		x			x		x	x	x
Quantitative immunoglobulins (IgA, IgG, IgM, and IgE)			x					x		x
PCL-5	x		x	x		x		x		x
SCID-5	x									
LEC-5	x									
CAPS-5 (administered by central rater)		x ^h				x		x		x
CGI-S			x			x		x		x
CGI-C						x		x		x
PGI-S			x			x		x		x
PGI-C						x		x		x

Table 1 Schedule of Activities (cont.)

	Screening	Pre-Rand. Visit	Blinded Treatment Period						Safety Follow-Up ^a	Early Discont. ^{b, c}
Week			0	2	4 ^d	6	9 ^d	12	14	
Study Day(s)	-28 to -1	-7 to -1	1	14	28	42	63	84	98	
Visit window (days)				±3	±3	±3	±3	±3	-3/+7	
Beck Anxiety Inventory			x			x		x		
Pittsburgh Sleep Quality Index			x			x		x		
PHQ-9			x			x		x		x
C-SSRS ^y	x	x	x	x	x	x	x	x	x	x
SDS			x			x		x		
CPFQ			x			x		x		
Computerized cognitive battery		x ^h		x		x		x		x
Wearable heart rate, step count, and sleep monitoring device (e.g., OURA™ Ring)		x ^z	x	x	x	x	x	x		x
Previous and concomitant medications ^{aa}	x		x	x	x	x	x	x	x	x
Adverse events ^{bb}	x	x	x	x	x	x	x	x	x	x
Study drug dispensation ^{cc}			x			x				
Study drug accountability				x	x	x	x	x		x

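### The Child-Pugh stop in Section 7.1.1 can turn on INR after an abnormal Week 6 panel, but nothing orders that INR, and the printed INR bands leave a gap

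*Combined protocol and SAP*

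**What the plan says.** **The stop.** Section 7.1.1: "Discontinuation of study treatment is also required if the participant experiences moderate or severe hepatic impairment, defined as Child-Pugh class B" or class C. Section 7.1 lists, among the grounds on which treatment must end permanently, "Specific events that are described in Sections 7.1.1, 7.1.2, 7.1.3, and 7.1.4".

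**The score.** Section 7.1.1 sends the reader to Appendix 8, where the class comes from "employing the added score of the 5 parameters described above": encephalopathy, ascites, bilirubin, albumin and INR. On timing, Appendix 8 says only that the "parameters to determine Child-Pugh classification for each participant will be collected at Screening". The same table serves eligibility. Section 5.2 excludes "Moderate or severe hepatic impairment defined as Child-Pugh class B" and class C.

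**The schedule (Section 1.3, Table 1).** The row "Coagulation ^m" is marked at Screening, Week 12 and early discontinuation. Its footnote reads "Coagulation assessments include INR, aPTT, and PT". The row "Full serum chemistry ^x", which holds bilirubin and albumin, is marked at Screening, Weeks 0, 6, 12 and 14, and early discontinuation.

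**The concern.** A mandatory stop needs an input that the schedule does not supply when the stop could matter. Week 0 chemistry is pre-dose and Week 12 closes the treatment period. Week 6 is therefore the only scheduled on-treatment chemistry panel that can still stop dosing, and INR is not drawn with it. The early discontinuation INR follows the decision to stop, so it cannot trigger it.

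Other safety rules in the protocol name their confirming test: a timed repeat for hs-cTnT (Section 7.1.4), a second sample for low ANC (Section 7.1.3) and a repeat ECG for QTcF (Section 8.2.4). The Child-Pugh stop names none. A site may hold an abnormal Week 6 panel and be unable to say whether the required stop applies, and a monitor could not verify it either.

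**Working it through.** **Inputs.** Appendix 8: five items, 1 to 3 points each; class B is 7 to 9, class C is 10 to 15. Table A8-1 bands:
- bilirubin <2, 2 to 3, >3 mg/dL
- albumin >3.5, 2.8 to 3.5, <2.8 g/dL
- INR <1.7, 1.7 to 2.3, >2.8

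Table 1: Week 6 is Day 42 and Week 12 is Day 84.

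**1. Reproduce the scale.** Minimum 5 × 1 = 5; maximum 5 × 3 = 15, which matches the stated top of class C. The stop applies at a total of 7 or more.

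**2. When INR decides.** Let S be the sum of the four non-INR items. Total = S + INR points.

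| S | INR 1 point | INR 2 points | INR 3 points | Stop without knowing INR? |
|---|---|---|---|---|
| 4 | 5 | 6 | 7 | undecided |
| 5 | 6 | 7 | 8 | undecided |
| 6 | 7 | 8 | 9 | yes |
| 7 to 12 | 8 or more | 9 or more | 10 or more | yes |

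At S = 4 all four other items are at their lowest score, so a stop needs an isolated 3-point INR. S = 5 is the practical case: exactly one of the four items scores 2.

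**3. A Week 6 example.** ALT and AST not above 3×ULN, so the rule in A3-7.6 is not met. Bilirubin 1.5 mg/dL (1) + albumin 3.2 g/dL (2) + no ascites (1) + no encephalopathy (1) = 5.
- INR <1.7: 5 + 1 = 6, class A, no required stop.
- INR 1.7 to 2.3: 5 + 2 = 7, class B, required stop.
- INR above 2.3: 5 + 2 = 7 or 5 + 3 = 8, class B whichever band is meant.

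**4. Exposure.** Scheduled on-treatment INR samples before Week 12: 0. Remaining dosing: 84 − 42 = 42 days, and 42/84 = 50% of the treatment period. This is an upper limit per participant. The documents give no rate for such cases.

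**5. The gap in the INR bands.** The bilirubin and albumin bands are contiguous; the INR bands are not. An INR of 2.5 has no points as printed. With S = 4, scoring it 2 gives 6 (class A) and scoring it 3 gives 7 (class B). That difference decides both entry under Section 5.2 and stopping under Section 7.1.1. With S = 5 the total is 7 or 8, so the gap does not matter.

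**6. What a reflex trigger catches.** There are four ways to reach S = 5, one for each item scoring 2. A trigger on bilirubin or albumin at 2 or more points catches two of them directly. The other two need slight ascites or encephalopathy grade 1 or 2, which are clinical findings. A trigger of this kind does not look for an isolated raised INR at S = 4.

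**The case against.** The rule is written for a clinical event, and Appendix 8 describes the score as a classification of chronic impairment. Nothing orders a Week 6 score. That stands. A reader might infer that the protocol requires serial scoring and that the schedule breaks its own rule; the documents do not say so.

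A reader might also infer that everyone is exposed, since every eligible participant starts with S at 4 or 5. That does not follow. S = 4 is simply a participant with nothing wrong on the other items.

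Entry criteria lower the risk further. Section 5.2 also excludes viral hepatitis on serology (with an HBV DNA route for core-antibody positives), coagulopathies, recent alcohol or substance use disorder, and confirmed clinically significant chemistry or coagulation abnormalities. Section 7.1.1 reports no evidence of a liver effect.

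Safeguards remain. Section 7.1.1 requires a stop for lesser abnormalities when the investigator thinks it best for the participant. Section 8.2.5 has clinically significant values repeated and, if they persist, the cause sought. Appendix 2 allows extra tests at any time. A3-3.4.1 obliges medically indicated follow-up of an adverse event. So the tempting reading that the stop cannot be applied at Week 6 is too strong.

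What these safeguards do not do is name INR. Section 8.2.5 repeats the abnormal test, A6-2.5 calls for coagulation tests after bleeding only, and the rest depends on site judgment. The minimum content of the limited Week 6 examination (Section 8.2.1) does not list the abdomen, so ascites may also go unchecked.

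A last objection concerns the remedy. An automatic stop when bilirubin, albumin and INR total 5 would be wrong. Anticoagulants are not named in Section 6.8.3. With INR 2.5 on an anticoagulant scored 3, and the other two items at 1, the sum is 5 with no liver disease. That objection is accepted.

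**Conclusion.** The point holds in a narrow form. When an abnormal Week 6 bilirubin or albumin brings the other four items to 5, INR alone separates continued dosing from a required permanent stop, and the plan does not order it. The consequence is at most 42 further days on drug for a participant who has moved to class B, in a trial of about 30. Cases should be rare, so this is a small gap in applying a safety rule. It does not threaten the efficacy results.

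The conclusion assumes that the Table 1 columns are read correctly and that the site does not order an INR on its own initiative. The point about the bands assumes that Table A8-1 reads in the source as it is printed here; the documents do not show whether 2.3 or 2.8 is the wrong figure. Its effect on eligibility is limited further by the separate exclusion for clinically significant coagulation abnormalities.

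**What to change.** 1. In Section 7.1.1 and Appendix 8, add: whenever an on-treatment bilirubin or albumin scores 2 or more points, or ALT or AST is above 3×ULN, obtain a reflex INR, assess ascites and encephalopathy, and record the full Child-Pugh score.
2. State that the stop applies to the full five-item score when the abnormality has no non-hepatic explanation, such as anticoagulant use. Do not use an automatic stop on the three laboratory items alone.
3. In Table A8-1, make the INR bands contiguous by changing the 3-point band to >2.3, after checking the source table. This is the cautious choice because it gives unscored values the higher points.

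Cost: a few extra INR tests, possibly an unscheduled check for ascites and encephalopathy once the Week 6 results are back, and short wording changes. No scheduled visit is added. An isolated raised INR with normal bilirubin, albumin and transaminases would still go unsought; that is acceptable given how unlikely it is.
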